A sample of 200 HCPs will be surveyed. Given the average 10% response rate obtained in previous similar surveys, it is expected that approximately 2000 HCPs from approximately 6 European countries combined will be invited to participate. This estimate is in line with the low response rate reported for similar surveys in the literature (Agyemang et al. 2017).

Data Analysis

The statistical analysis will be conducted using SAS (Version 9.4 or above).

Results will be presented in total, by country, and by speciality (i.e., oncologist and pulmonologist), if applicable in the target country.

Continuous variables will be presented by the number of valid cases, mean, standard deviation, median, Q1, Q3, minimum, and maximum.

Categorical variables will be presented as the total number and relative percentage per category. Confidence intervals of 95% will be calculated as appropriate.

Individual awareness scores will be descriptively analysed and reported as percentages. Awareness level will be calculated as the mean of the individual scores.

Individual knowledge scores and individual HCP clinical practice scores will be calculated as the percentage of correctly answered survey questions; scores will range from 0 to 100% with 100% representing the percentage of all knowledge questions and

clinical practice questions being answered correctly, respectively. Knowledge level and clinical practice level will be calculated as the mean of individual scores.

Calculations will firstly be performed on raw data in total, by speciality, and by country; subsequently results will be weighted according to the real proportion of HCPs in each country to accurately reflect the population the survey seeks to measure.

Possible selection bias will be assessed by comparing the distributions of available characteristics (e.g., country, type of setting, and speciality, if applicable and feasible) between respondent and non-respondent HCPs.

A successful outcome on the effectiveness of risk minimisation measures is defined a priori by the following target levels:

- Proportion of HCPs being aware of the important identified risk and related minimisation measures for Alecensa (Question Q2 and Q3 of HCP questionnaire) – Success: ≥75%
- 2. Proportion of HCPs knowledgeable about the important risks, specific monitoring, dose modification (Questions Q5 to Q8 of HCP questionnaire) Success ≥60%

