- HCPs can also choose to participate in the survey by phone in the local language. In this case, an appointment for a phone interview will be scheduled with them

- HCPs who self-report having treated patients with Alecensa at least once in the 6 months prior to the study and are not employed by a pharmaceutical company,
 , or by regulatory bodies will be eligible to complete the survey. Both parameters are included as screening questions in the questionnaire
- Once HCPs have passed the screening questions of the questionnaire, they are moved through the questions one question at a time. HCPs can only progress to the next question when the previous question was answered. Only wholly completed questionnaires can be submitted
- If the questionnaire is not completed within one week, the HCPs will be sent a reminder by email one week after the link was sent to them
- If the study sample size is not achieved in the stratum (speciality/country), a second reminder by phone will be conducted 1.5 weeks after the link has been sent
- If the questionnaire is still not fully completed, a third and final reminder will be sent to the HCPs by email approximately three weeks after the start of the survey

If necessary, i.e., if the minimum number of needed responders is still not reached, the recruitment will be continued to achieve the study sample size-in a specific stratum.

A HCP will be considered as unreachable if he/she has been contacted between 3 and 5 times without any answer being received.

For each HCP of the sample, the number of contacts, and the date and time when he/she completed the web questionnaire will be recorded. The recruitments in each stratum (HCP speciality/country) will be stopped when the target is reached. If the files have been exhausted in any particular stratum, the recruitments in this stratum will be prematurely ended and a strategy will be determined to adjust the sample size with associated weighting.

The number of HCPs passing the screening questions, incidence rate, and the survey response rate will be monitored regularly by **series**. If the survey response rate or incidence rate is too low, the recruitment may be undertaken in additional countries.

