8.5 STUDY SIZE

8.5.1 Study size calculation

The sample size formula based on the normal approximation to the binomial is the following:

$$n = \frac{P \cdot (1-P) \cdot \left(Z_{1-\alpha/2}\right)^2}{e^2},$$

Where P is the expected proportion, e is one half the desired width of the confidence interval, and $Z1-\alpha/2$ is the standard normal Z value corresponding to a cumulative probability of $1 - \alpha/2$ (e.g., if $\alpha = .05$ then Z = 1.96).

The proportions of interest (p) here are the proportions mentioned under specific objectives above. As p is not known in advance, we consider it to be 50% (maximum uncertainty). Such a hypothesis yields the most conservative i.e., the largest sample size. For example, the required sample size would be 100 for precision levels of 10%. Table 2 below provides precision of the estimate (width of 95% CI around the estimate) for a range of sample sizes.

Sample Size	Statistical Precision (%)
100	±9.8
150	±8.0
200	±6.9
250	±6.2
300	±5.7
350	±5.2
400	±4.9

For this survey, a sample size of approximately 200 completed questionnaires aggregated across the target countries is being considered, which is based on both statistical and practical considerations. With a sample size of 200, the statistical precision around the estimate will be $\pm 6.9\%$; the precision will increase with larger sample sizes. It is to be noted that the final survey sample size will depend on HCPs' willingness to participate in the survey. While the target is 200 respondents, all completed responses received by the cut-off date will be included in the analysis.

Assuming that the survey response could be as low as 10%, about 2,000 HCPs will be invited to participate in this survey in order to increase the number of HCPs passing the screening questions and the likelihood that at least 200 HCPs fill out the questionnaire This estimate is in line with the low response rate reported for similar surveys in the literature (Agyemang et al. 2017).

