All questions in the questionnaire will be mandatory and cannot be skipped. Questionnaires can only be submitted when fully completed. Therefore, missing data are not expected to occur.

Entering erroneous information is only possible for open questions. These nonadmissible values (if any) identified after database lock will be excluded from analysis.

Analysis of HCP Participation Rate

The following different cases will be distinguished:

- HCPs who refused to participate (R): HCPs explicitly mentioned their refusal to participate
- HCPs with partial questionnaires (P): HCPs who clicked on the link provided in the invitation email, who began the questionnaire but never submitted it
- HCPs with completed questionnaire (C): HCPs who completed the entire questionnaire
- Contacted HCPs: HCPs who was reached by phone or who received a web link to the online survey via email. For survey invitations issued via postal mail the assumption will be made that if mail is not returned, HCP will be considered "contacted" = C+P+R
- HCPs who agreed to participate: HCPs willing to participate in the survey (e.g., by phone or by clicking on the link provided in the invitation email) = P+C

The HCPs' participation in the survey will be examined as follows (adapted from: *American Association for Public Opinion Research 2016*):

- Response rate = $\frac{C}{C+P+R}$
- Refusal rate = $\frac{R}{C+P+R}$

The participation rates will be presented by country and by speciality.

Questionnaire analysis

Analysable questionnaires are those completed and submitted by the participants on the web or by phone. If the questionnaire is just filled on the web but not submitted, or if the name and surname of the participant is disclosed, the questionnaire will not be analysed and will be discarded.

The proportions of correct and appropriate answers to selected questions asked in the questionnaire will be expressed among HCPs who provided answers to those questions.

Awareness questions (Questions Q2 to Q3 of HCP questionnaire: Individual HCP awareness scores will be descriptively analysed and reported as percentages. HCP awareness level will be calculated as the mean of the individual scores.

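### The response rate C/(C+P+R) leaves out HCPs who receive the link and never answer, contradicts the protocol's own definition of contacted, and is not comparable with the 10% planning rate

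*Protocol*

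**What the plan says.** Section 8.7 (Analysis of HCP Participation Rate) sorts HCPs into three groups. R is a refusal: "HCPs explicitly mentioned their refusal to participate". P is an HCP who clicked the link, "who began the questionnaire but never submitted it". C completed the whole questionnaire. The same list has this entry: "Contacted HCPs: HCPs who was reached by phone or who received a web link to the online survey via email". It adds that a postal invitation that is not returned also counts as contact, and then equates contacted with C+P+R. The response rate is C/(C+P+R) and the refusal rate is R/(C+P+R). Both are to be shown by country and by speciality.

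Section 8.4.2 recognises HCPs who never react: "A HCP will be considered as unreachable if he/she has been contacted between 3 and 5 times without any answer being received". It also places the eligibility questions inside the questionnaire.

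For planning, the Synopsis (Study Size) says "Given the average 10% response rate obtained in previous similar surveys", and Section 8.5.1 says "Assuming that the survey response could be as low as 10%, about 2,000 HCPs will be invited to participate in this survey".

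**The concern.** The verbal definition and the equation cannot both hold. Someone who was sent the link and stayed silent is contacted under the words, but did not complete, did not begin and did not explicitly refuse. The equation removes that person from the denominator of both rates. The planning rate, under the same name, keeps them in.

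Response and refusal rates are the first variables listed in Section 8.3. In a volunteer survey they are one of the figures by which a reader judges non-response. Because they are reported by stratum, different degrees of silence between countries or specialities would make strata look different, or alike, for reasons unrelated to completion among those invited. Section 8.4.2 also has the response rate monitored, with recruitment in additional countries possible if it is too low. If the Section 8.7 formula is used for that monitoring, silence would not register.

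A second gap is that HCPs who fail the screening questions have no stated category.

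**Working it through.** **Inputs.** Target completes C = 200 and about 2,000 invited (Section 8.5.1). Planning response rate 10% (Synopsis and Section 8.5.1). Formula C/(C+P+R) (Section 8.7). The number of silent invitees and of screen-outs is not given, so both are varied as assumptions.

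**Step 1: the plan's own figure.** Invited = 200/0.10 = 2,000, as stated. The planning rate is therefore completes over all invited, 200/2,000 = 10%.

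**Step 2: direction.** C, P and R are all drawn from the invited HCPs, so C+P+R cannot exceed the number invited. Hence C/(C+P+R) is at least C/invited, with equality only if no invited HCP falls outside the three groups.

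**Step 3: size.** Take the planned outcome, 200 completes of 2,000 invited, leaving 2,000 − 200 = 1,800 non-completers. Let s be the share of these who never answer. All other non-completers are counted in P or R. Then

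rate = 200 / (200 + 1,800 × (1 − s)).

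| Silent share s (assumed) | Silent | P+R | C+P+R | C/(C+P+R) | Completes/invited |
|---|---|---|---|---|---|
| 0% | 0 | 1,800 | 2,000 | 10.0% | 10% |
| 25% | 450 | 1,350 | 1,550 | 12.9% | 10% |
| 50% | 900 | 900 | 1,100 | 18.2% | 10% |
| 75% | 1,350 | 450 | 650 | 30.8% | 10% |
| 90% | 1,620 | 180 | 380 | 52.6% | 10% |

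The refusal rate is inflated by the same factor, 2,000/(C+P+R). At 75% silent this is 2,000/650 = 3.1.

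**Step 4: screen-outs.** The text does not settle where they go. Assume 100 of them.

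- With 1,350 silent, the remaining P+R is 1,800 − 1,350 − 100 = 350. Screen-outs counted as P: 200/(200 + 350 + 100) = 30.8%. Left out: 200/(200 + 350) = 36.4%.
- With 1,620 silent, the remaining P+R is 80. Counted as P: 200/380 = 52.6%. Left out: 200/280 = 71.4%.

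Counting screen-outs as P thus lowers the rate. It also places them among those who agreed to participate (P+C in Section 8.7) but did not complete, although they were not eligible to do so.

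**Step 5: after the repair.** Completes over invited is 200/2,000 = 10.0%. With known screen-outs removed as ineligible it is 200/1,950 = 10.3% for 50, 200/1,900 = 10.5% for 100 and 200/1,850 = 10.8% for 150.

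**The case against.** The strongest case on the other side is that these are descriptive participation figures. They enter none of the success criteria in Section 8.7, the weights in Section 8.5.3 or the precision calculation in Section 8.5.1, and the step of adding countries is discretionary. Non-response is also not ignored elsewhere. Section 8.7 plans a comparison of respondents with non-respondents, Section 8.9 discusses unseen invitations and limited generalisability, and Section 8.4.2 records the number of contacts per sampled HCP. Completes over invited could be derived from what is already tracked. All of this stands, and it limits the severity. It does not repair a definition and a formula that contradict each other, or one name used for two quantities.

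A reader might infer a several-fold overstatement. The documents do not support any particular multiple, because the silent share is not given. A reported rate of 80%, for instance, needs P+R = 50, so 1,750 of 1,800 non-completers (about 97%) silent. If screen-outs are counted as P, the formula also cannot exceed the screening pass rate.

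A reader might also infer that the missing screen-out category inflates the rate. That follows only if screen-outs are dropped. If they count as P, the effect runs the other way. Section 8.7 does not say which applies, and an HCP screened out by phone never clicked a link.

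**Conclusion.** The point holds as a defect in the reporting definition, of moderate severity. Section 8.7 contradicts itself on who is contacted. Its response rate omits silent invitees, can never fall below completes over invited, and is not comparable with the 10% planning rate. The refusal rate shares the fault. These conclusions follow from the text alone.

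The size does not. For the planned 200 of 2,000, the formula gives 12.9% to 52.6% instead of 10% if 25% to 90% of non-completers are silent, and that share is an assumption. The unplaced screen-outs add an uncertainty that can pull in the opposite direction and cannot be relied on to cancel the first error.

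It would be wrong to infer that the number of invitations is miscalculated, since 200/0.10 = 2,000 is consistent, or that any conclusion on awareness, knowledge or practice changes. What is affected is the judgement of non-response, overall and by stratum, and the monitoring of response in Section 8.4.2 if it uses this formula.

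**What to change.** Amend Section 8.7 before data collection:

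- Define contacted consistently as all HCPs sent an invitation or reached by phone, and delete the equation with C+P+R.
- Add two categories: no answer/unreachable, tied to the rule in Section 8.4.2, and screened out as ineligible, stated not to be part of P.
- Report completes over invited as the response rate, which is the planning basis. Optionally show it also with known ineligible HCPs removed.
- Put the same denominator under the refusal rate.
- Keep C/(C+P+R) only under the name of a cooperation rate among HCPs who reacted.
- State in Section 8.4.2 that the monitored response rate is the one on the invited basis.

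A rate that discounts silent HCPs by the observed screening pass rate is optional. It assumes that those who ignored the invitation would pass screening as often as those who opened it, it treats refusers as eligible, and it would not be comparable with the 10%.

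The cost is a change of wording. Contacts per HCP and the number passing screening are already tracked. The price is a less favourable reported response rate.

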For this study, physicians in oncology and pulmonology will be considered. Due to the indication treatment of adult patients with ALK-positive NSCLC, they are the main prescriber group of Alecensa and, therefore, the target audience of the RMM.

All HCPs (i.e., oncologists and pulmonologists) in the study countries who can be identified as potential prescribers of Alecensa and have not provided their general opt out will be considered as the target population. The HCPs will be randomly selected from the database, on an ongoing basis keeping a representative regional

spread, to participate in the survey until the target number of HCPs for that country is reached or the list is exhausted.

Inclusion criteria:

HCPs (i.e., either oncologists or pulmonologists) must meet the following criteria for study entry:

 HCPs must have treated patients (newly initiated or repeated administration/prescription) with ALK-positive NSCLC with Alecensa according to local label at least once in the 6 months prior to taking the survey

Exclusion criteria:

Inactive and retired HCPs (when documented information is available to identify them) will be deleted from the contact lists before randomization. HCPs who meet any of the following criteria will be excluded from study entry:

- HCPs who are not involved in patient treatment
- HCPs who may have conflicts of interest with the survey (i.e., HCPs employed by regulatory bodies, pharmaceutical industries)
- Employment by Roche, or any research organization/vendor contracted by Roche to administer the survey

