8.5.2 Sampling Plan

For each selected country, the sample survey will include HCPs identified and recruited from the **selected** list. The **selected** database covers above 90% of the specialities of

interest (i.e., oncologists and pulmonologists) in the target countries (i.e., Austria, Belgium, Germany, Spain, Sweden, and the UK).

A screening question will check whether the physician did ever treat patients with Alecensa in the last 6 months prior to the survey and can therefore be considered for the survey.

With respect to the indication for Alecensa the survey will be deployed amongst oncologists and pulmonologists. The split between the two will depend on who provides care for NSCLC patients in each respective country.

As per sample size defined above and the number of selected countries, the following potential split of sample into strata of the HCPs by country is planned thereby taking into account the size of the country and the HCP universe size (see Table 3)

This table is indicative and will be adjusted according to the final list of countries included and the responsive HCP per strata. It is aimed to have at least 20 completed questionnaires per country.

Planned Country	Overall Number of Completed Questionnairesª	Universe Oncologists ^ь	Universe Pulmonologists ^ь
Germany	50	2900	2400
United Kingdom	45	2700	2500
Spain	45	2300	N/A¢
Austria	20	300	600
Belgium	20	500	700
Sweden	20	600	300
Total	200	N/A	N/A

Table 3 Split of Sample by Country According to a Sample of 200 HCP Questionnaires

^aThe split between specialties depends on the involvement of specialties in the management of advanced lung cancer patients in the different target countries and may be subject to change.

^bUniverse: Numbers of oncologists/pulmonologists in the country according to **according to according (version June** 2018)

^cOnly oncologists are relevant in the treatment of NSCLC in Spain

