Knowledge questions (Questions Q5 to Q8 of HCP questionnaire): For each question, the number and percentage of HCPs answering correctly each subquestion will be presented. Subsequently, individual HCP knowledge scores will be calculated as the percentage of correctly answered knowledge questions; scores will range from 0 to 100% with 100% representing the percentage of all knowledge questions being answered correctly. HCP knowledge level will be calculated as the mean of individual scores.

Clinical practice questions (Questions Q9 and Q10 of HCP questionnaire): For each question, HCPs answering correctly each sub-question will be presented. Subsequently, individual HCP clinical practice scores will be calculated as the percentage of correctly answered survey questions; scores will range from 0 to 100% with 100% representing the percentage of all clinical practice questions being answered correctly. HCP clinical practice level will be calculated as the mean of individual scores.

In a first step, calculations will be performed on raw data. No projection factor will be applied to generalize the results to the entire prescribers' universe. As a consequence, the line "Overall - unweighted results" will show only the results observed on the overall sample and will not reflect the countries' universe since this sample is not proportional to the size of the lists in each country.

In a second step, the results will be weighted according to the real proportion of HCPs in each country in order to accurately reflect the population that the survey seeks to measure.

Possible selection bias will be assessed by comparing the distributions of available characteristics (e.g., country, type of setting (hospital or office-based), and speciality, if applicable and feasible) between respondent and non-respondent HCPs.

Moreover, the profile of HCPs with incorrect answers could be identified and described with all available relevant covariates collected in the survey (e.g., country, duration of practice, type of setting, and speciality) and past experience with Alecensa (number of patients treated).

Assessment of success

A successful outcome on the effectiveness of risk minimisation measures is defined a priori by the following target levels:

- Proportion of HCPs being aware of the important identified risk and related minimisation measures for Alecensa (Question Q2 and Q3 of HCP questionnaire) – Success: ≥75%

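### The selection-bias check sets screened Alecensa prescribers against non-respondents of unknown eligibility, so a difference need not mean bias and no difference does not exclude it

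*Protocol*

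**What the plan says.** **The check.** Protocol Section 8.7 (Questionnaire analysis) says "Possible selection bias will be assessed by comparing the distributions of available characteristics". The examples given are "country, type of setting (hospital or office-based), and speciality, if applicable and feasible) between respondent and non-respondent HCPs".

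**Who is invited.** Section 8.2.2 defines the target population as "All HCPs (i.e., oncologists and pulmonologists) in the study countries who can be identified as potential prescribers of Alecensa". Being a potential prescriber rests on speciality, not on known use of the product.

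**Who can complete.** Under Section 8.4.2, those eligible are "HCPs who self-report having treated patients with Alecensa at least once in the 6 months prior to the study" who also have no excluded employer, and "Both parameters are included as screening questions in the questionnaire". Section 8.5.2 repeats this: "A screening question will check whether the physician did ever treat patients with Alecensa in the last 6 months". Eligibility is thus learned only from HCPs who open the questionnaire or take the phone interview.

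**How numbers are controlled.** Section 8.4.2: "The recruitments in each stratum (HCP speciality/country) will be stopped when the target is reached". Table 3 gives indicative country targets (Germany 50, UK 45, Spain 45; Austria, Belgium and Sweden 20 each) but no numeric targets by speciality. Section 8.5.3 then weights by country and speciality.

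**What is already recorded.** Section 8.4.2: "For each HCP of the sample, the number of contacts, and the date and time when he/she completed the web questionnaire will be recorded".

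**The concern.** The two groups differ by design in something other than willingness to answer. Completers are self-declared recent prescribers. Non-respondents are a mixture of prescribers who did not answer and HCPs who have no reason to. A contrast in speciality or setting between these groups may only show where Alecensa is prescribed.

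Country has a second problem. The respondents' country mix is set largely by targets and stopping rules, and weighting later adjusts for it. The same holds for speciality wherever a target is set. These are the factors on which a comparison says least about self-selection.

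The participation classes in Section 8.7 (refused, partial, completed) have no category for HCPs who are screened out, so it is also unclear on which side of the comparison they fall.

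At stake is how far the three success proportions (targets of 75%, 60% and 75%) can be trusted in a volunteer survey. Section 8.9 admits volunteer selection as a limitation but does not mention the mismatch in eligibility.

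**Working it through.** **The plan's own figures.** The protocol gives no figure for this check. The related one reproduces: 200 completed questionnaires / 0.10 = 2,000 invitations. Section 8.5.1 ties that number partly to getting enough HCPs past the screening questions, so the plan itself expects ineligible invitees.

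The prescribing (eligibility), response and setting values below are assumptions; the protocol gives only the 10% figure. P-values are Pearson chi-square, used as a gauge; the protocol names no test.

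**1. Speciality, Germany (Table 3: 2,900 oncologists, 2,400 pulmonologists).** Oncologists are 2,900/5,300 = 55% of the list. Take invitations at random from the list, equal response among prescribers, and no speciality target. The oncologist share of completers is then 2,900a / (2,900a + 2,400b), where a and b are the prescribing rates of oncologists and pulmonologists.

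- a = 30%, b = 30%: 870/1,590 = 55%
- a = 30%, b = 20%: 870/1,350 = 64%
- a = 30%, b = 10%: 870/1,110 = 78%
- a = 20%, b = 30%: 580/1,300 = 45%

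The planned comparator is non-respondents, not the list, but the two are close. With 30%/10% and 25% response among prescribers, the expected non-respondents are in the ratio 2,900 × 0.925 = 2,682.5 to 2,400 × 0.975 = 2,340, so 2,682.5/5,022.5 = 53% are oncologists. The contrast would be 78% v 53% with no self-selection.

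**2. Country, with equal response among prescribers.** Invitations per country = target / (eligibility × response), scaled to 2,000; non-respondents = invitations − target.

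- Equal eligibility everywhere: both groups split 25/22.5/22.5/10/10/10% (p = 1), so no difference.
- Germany and Austria 1.5 times the rest: Germany is 25% of respondents v 18.2% of non-respondents (p = 0.13).
- Germany and Austria twice the rest: the yield is 16.5% v 8.25%. Germany needs 50/0.165 = 303 invitations, leaving 253 of 1,800 non-respondents: 25% v 14.1% (p = 0.0001).

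Unequal eligibility is plausible, because Table 1 sales shares per listed HCP differ about 7.5-fold across the six countries. Sales are only a proxy for the number of prescribers.

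**3. Setting.** Assume that 70% of the list is hospital-based, that 45% of hospital and 28.3% of office HCPs are eligible, and that 25% of the eligible respond. Completers: 0.7 × 0.45 × 0.25 = 0.0788 hospital and 0.3 × 0.283 × 0.25 = 0.0212 office, i.e. 78.8% hospital-based. Non-respondents: (0.7 − 0.0788)/(1 − 0.1000) = 69.0% (p = 0.004). Response was equal throughout.

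**4. Bias that the check would not show.**

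- *Masking by eligibility.* Let eligibility be 60% in Germany and Austria and 20% elsewhere, with response 16.7% and 50%. The yield is 10% in every country, so the distributions match exactly (p = 1) despite a threefold difference in response. Among eligible non-respondents, Germany is 250/480 = 52%, against 25% of respondents.
- *Bias within strata.* If aware HCPs respond k times as often as unaware ones, in the same way in every country, speciality and setting, observed awareness is tk/(tk + 1 − t) for true awareness t. For t = 65%, k = 1.5 gives 0.975/1.325 = 73.6% and k = 2 gives 1.30/1.65 = 78.8%. For t = 70% the results are 77.8% and 82.4%. Three of these four cases reach or exceed the 75% target although true awareness is below it.

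**The case against.** The case against is substantial, and several parts of it stand.

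- **Quotas alone.** A reader might set the targets against the list (Germany 50/200 = 25% v 5,300/15,800 = 33.5%; Spain 45/200 = 22.5% v 2,300/15,800 = 14.6%) and infer that the quotas by themselves must produce a difference. The documents do not support that. Listed HCPs who were never invited are not non-respondents. Recruitment is random and ongoing until each target is met, so invitations can follow the targets. With equal eligibility and response no difference then appears (step 2, first case).
- **All factors fixed by quota.** This too goes further than the text. Setting is not a stratum or quota anywhere; it suffers only from the eligibility mismatch. Speciality has no numeric target, and the Table 3 split is indicative.
- **The only safeguard, against 90% non-response.** Neither half of this reading holds. Response and refusal rates are reported by country and speciality, screening passes and incidence are monitored, results are weighted, and Section 8.9 restricts generalisation. The 10% yield may include ineligible invitees, so 90% is not shown to be non-response among prescribers.
- **Detail for the SAP.** The factors are examples, subject to feasibility, and respondent is not defined as completer. Other list variables and a within-stratum comparison are not excluded. An SAP could settle these points. Even so, the protocol itself names the two groups without reference to eligibility, and adding variables does not cure that.
- **The remedy is partial.** Prescribers may be likelier to open a survey about this product, and never-answerers still have unknown eligibility. This is correct and should be stated in the report.

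**Conclusion.** The concern holds in a conditional form. As stated, the check mixes prescribing status with willingness to answer, and on country (and on speciality where a target is set) it also mixes in the allocation of invitations and the recruitment stops. It can mislead in either direction. It is not certain to show a spurious difference.

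No single size can be given. On the assumed prescribing rates, the oncologist share of German completers runs from 45% to 78% against 55% of the list, with identical response in both specialities; at equal prescribing rates there is no distortion. A null result is no firmer, since a threefold response difference can be hidden completely, and selection on awareness within strata leaves list characteristics untouched. All of this assumes that respondents means completers. If the plan meant everyone who answered the screener, much of the problem goes, but the protocol does not say so.

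**What to change.** Restate the check in Section 8.7 before fieldwork:

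1. Within each country-by-speciality stratum, compare all HCPs who answered the screener, passes and screen-outs together, with invited HCPs who never answered, on list characteristics such as setting and region. This takes the eligibility filter off the responding side, and conditioning on stratum takes out the targets and stops.
2. Give screen-outs their own participation class and report them separately by stratum.
3. Within strata, compare the awareness, knowledge and practice scores by number of contacts (early v late responders). This is the only part that looks at the scores themselves. It must be done within strata, because the phone reminder is used only where a stratum is short of its target and closed strata lose their late responders.
4. State in the report that the eligibility of never-answerers is unknown, so the check reduces the ambiguity without removing it.

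The cost is a little more analysis. Contact counts and web completion times are already to be recorded. The screening result and the list characteristics need to be kept for screen-outs as well as completers, and the contact count has to be carried into the analysis file without identifying the HCP.
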